Participants will be captured by an undergraduate student who will not participate in the data collection. He will be solely responsible for capturing participants, applying the eligibility criteria using a checklist (Appendix 1) and requesting the signature of the IC. This stage will take place at the entrance to the operating room where patients and caregivers, coming from the outpatient clinic after weighing and measuring, await surgery. Subsequently, it will deliver to the principal researcher the envelope referring to the participant, which will contain the group to which he / she has been allocated.

Allocation will be by sequentially numbered, otherwise identical, sealed envelopes, each containing a 2 inch by 2 inch paper with a written code that will designate the intervention group or the comparative group. There will be no detectable differences in size or weight between intervention group envelopes and comparative group envelopes. Envelopes will be opaque and opened sequentially only after the patient information assigned to them has been written to them. The envelope opening will occur before the patient enters the operating room so that the study setting can be set.

The lead researcher will be responsible for the entire procedure, along with the anesthesiologist responsible for the surgery. Data collection in turn will be performed by a student of scientific initiation responsible only for data collection without knowledge of the group to which the patient will be allocated (CPAP system will be selected before the student enters the room for collection).

A flowchart (CONSORT) will be completed with study progress throughout the phases of a two-group parallel intervention study (participant selection, intervention allocation, follow-up, and data analysis) (Figure 1).

All medical records of the participants involved in the study will be identified by self-adhesive labels containing the research name, registration number, study identification number and the group in which it was allocated.

Terms, Variables and Concepts

Control Variables (for sample characterization)

Age

Weight

Height

Sex

Physical state according to ASA

Surgery type

Independent Variable

CPAP Usage

Dependent Variables

Time between onset of apnea and 95% drop in oxyhemoglobin saturation (Time 1);

Oxyhemoglobin saturation on pulse oximetry during anesthetic induction at different times;

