Frequency of complications: laryngospasm, hypoxemia, bradycardia, cardiopulmonary arrest, death;

Time to recover oxyhemoglobin saturation levels in pre-apnea pulse oximetry (Time 2);

Procedures, tests, techniques and exams

Performing Anesthesia:

Patients selected for the study will be admitted to the operating room and will receive regular monitoring (cardioscope, oximeter, noninvasive blood pressure and capnography).

Inhalation induction will be with 8% sevoflurane, 60.5% inspired oxygen fraction under fresh gas flow of 4l / min (2l oxygen and 2l compressed air) until loss of eyelid reflex. The anesthetic concentration will then be reduced to 4%. A face mask coupled to the anesthesia machine will be used, fixed to the patient through an elastic band.

After adequate ventilation is verified through the correct positioning of the face mask and capnography curve present, peripheral venous access with venous catheter number 20, 22 or 24G will be obtained for hydration and propofol infusion at a dose of 3.5mg / kg to induce apnea in patients in both groups.

CPAP Realization

Patients will be submitted soon after monitoring the technique described on the envelopes delivered at the entrance to the operating room.

In the CPAP group, it will be applied to the anesthesia device (Dräger Fabius GS) using a circular system. This system consists of two corrugated tubes coupled at one end to a Y-piece, connected to the patient's face mask, and at the other end to the anesthesia machine which, in addition to providing fresh gas flow, has a carbon dioxide absorber called lime. soda. The latter allows the system to be circulated by removing CO₂ from the air supplied to the patient, warms and humidifies the gas mixture. A pressure relief valve (pop-off valve), which prevents gas loss by the patient-device system when closed, is an integral part of the anesthesia device. It has several markings (0-70cmH₂O), is manually manipulated and can be open (0cmH₂O), ie without any pressure being supplied to the patient's airway or closed. In the closed position, there will be continuous positive pressure being delivered to the patient's airway. The pressure that will be used in this group will be 10cmH₂O.

In the Open System group, the system will remain with the valve in the open position, ie 0cmH₂O.

In both groups, patients will spontaneously ventilate from the outset with the technique defined at the time of allocation.

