After the apnea begins, the time will be timed and periodically (every 10 seconds), the oxyhemoglobin saturation through the pulse oximeter will be recorded for a maximum time limit of five minutes in order to catch a minimum saturation of 95% in both groups.

The entire anesthetic procedure will be attended by the anesthesiologist who accompanies the patient and will be at his discretion as soon as the study is over.

Procedures for data collection

Data Collection Instrument

Data will be collected using a standard, pre-coded form for data entry into the computer (Appendix 3). Information on categorical variables will be pre-coded and continuous variables will be expressed at their own numerical value and only at the time of analysis will the results of some of these be categorized.

These forms will be properly stored in specific file folders, before and after typing and analysis, under the responsibility of the researcher, who will fill them out at different times, before, during and after the surgical procedure.

Data collect

Data will be collected by an independent researcher who will be present in the operating room, fill out the form with patient identification data and study variables and will not interfere with the anesthetic procedure to be performed.

The time from the moment of cessation of respiratory movements and decay of the capnography curve will be timed. The measurement will take place until the pulse oximetry is recorded at 95%. Assisted ventilation will then be instituted (in the Open System group, the pop-off valve will be manually closed to 10cmH₂O). At this time, there will be a new timing of the time until pulse oximetry reading of the value of 100% or the value obtained immediately before the beginning of apnea.

Data Processing and Analysis

Data Processing

Typing in the specific database created in the excel program will be performed twice, at different times and by different people, obtaining at the end a listing to correct any typing errors, under the supervision of the researcher himself.

In case of inconsistencies or lack of data when the listings are reviewed, the corresponding archived forms will be consulted, according to the patient's registration number.

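### The plan states that the data collector does not know the group but does not secure it: the collector is in the room with a marked valve set differently in each group, and nothing keeps it from view.

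*Combined protocol and SAP*

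**What the plan says.** **The blind.** Under Participant Capture and Follow-Up Procedures, the student who collects data does so "without knowledge of the group to which the patient will be allocated (CPAP system will be selected before the student enters the room"). No other means of masking is given. The same section has the lead researcher receive the envelope and take charge of the procedure together with the anesthesiologist. It also has each participant's medical record labelled with the allocated group.

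**The valve.** CPAP Realization describes a hand-operated pop-off valve on a 0-70 cmH2O scale: "It has several markings". It is used at 10 cmH2O in the CPAP group. For the comparison group, "In the Open System group, the system will remain with the valve in the open position", that is, at 0 cmH2O. The setting applies before apnea: "In both groups, patients will spontaneously ventilate from the outset with the technique defined at the time of allocation".

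**The measurement.** Data collect states: "Data will be collected by an independent researcher who will be present in the operating room". Time 1 starts at apnea: "The time from the moment of cessation of respiratory movements and decay of the capnography curve will be timed". It ends when the oximeter shows 95%. Assisted ventilation then begins and, "in the Open System group, the pop-off valve will be manually closed to" 10 cmH2O. Timing restarts at that point for Time 2.

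**The recorder.** Participant Capture and Follow-Up Procedures names a student, Data collect names an independent researcher, and Data Collection Instrument says that the researcher responsible for the forms completes them.

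**The concern.** Choosing the system before the collector enters conceals the adjustment, not its result. If the valve or a pressure reading is in sight, the collector can tell the group before timing starts. The collector is the only person whom the plan describes as unaware of the group once the envelope is opened, because those giving the treatment must know it.

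Two things are at stake. The first is observer bias in the part of Time 1 that needs judgement, the call that apnea has begun. The second is the report: the trial could be described as having a blinded assessor when the plan does not secure one. The second holds whatever the size of the first.

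**Working it through.** **Step 1. Valve position against the collector's presence.**

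| Period | CPAP group | Open System group | Collector |
|---|---|---|---|
| Spontaneous breathing | 10 cmH2O (CPAP Realization) | 0 cmH2O (CPAP Realization) | Enters after the system is selected |
| Apnea, Time 1 | 10 cmH2O (inferred) | 0 cmH2O, until 95% | In the room (Data collect) |
| Recovery, Time 2 | No change described | Closed by hand to 10 cmH2O | In the room |

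No sentence says outright that the CPAP valve stays at 10 cmH2O during apnea. It is inferred because the technique is in place from the start and the only later change described is to the Open System valve. On that reading the two positions differ throughout Time 1. No section mentions a screen, a cover for the valve or pressure display, or a fixed place for the collector.

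The closure at 95% comes after Time 1 has ended for that child. It can therefore reveal the group for Time 2 but cannot alter that child's Time 1.

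**Step 2. Reproduce the planned sample size.** Inputs from Sample size: 166 ± 47 s and 131 ± 39 s, 5% significance, 90% power. Sidedness is not stated; two-sided is assumed here.

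- Planned difference: 166 − 131 = 35 s.
- Sum of variances: 47² + 39² = 2209 + 1521 = 3730.
- n per group = (1.95996 + 1.28155)² × 3730 / 35² = 10.5074 × 3730 / 1225 = 31.99, rounded up to 32, or 64 in all.
- With 10% loss: 64 / 0.9 = 71.1, raised to 72 (36 per group).

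Both planned figures reproduce. A one-sided test would give 27 per group, so two-sided is the reading that fits.

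**Step 3. What a shift in called onset would do to Time 1.** The documents give no figure for such a shift, so b below is an assumed average between-group difference, in seconds, in when apnea is called.

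- SE = √(3730 / 32) = √116.56 = 10.80 s.
- Share of the planned effect = b / 35.
- Two-sided type I error, shift favouring CPAP = P(|Z + b/SE| > 1.96).
- Power, shift against CPAP = P(|Z + (35 − b)/SE| > 1.96).

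| b (s) | b/SE | Share of 35 s | Type I error | Power |
|---|---|---|---|---|
| 0 | 0 | 0% | 5.0% | 90% |
| 1 | 0.093 | 3% | 5.1% | 88% |
| 2.5 | 0.232 | 7% | 5.6% | 85% |
| 5 | 0.463 | 14% | 7.5% | 79% |

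The average shift needed to reach a 6% error is 0.295 × 10.80 = 3.2 s. To reach 10% it is 0.652 × 10.80 = 7.0 s.

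**Step 4. Time 2.** The documents give no mean or SD for it, so no comparable figure can be worked out.

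**The case against.** The strongest reply is that this is an operational detail left unwritten, not a contradiction. The plan commits to an unaware collector, confines that person to data collection and has the system set beforehand. Moreover, the outcome leaves little to judgement: Time 1 ends on an oximeter reading, and its start requires both that breathing movements stop and that the capnography curve decays, the second being an instrument trace.

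Most of this stands. The two-part criterion and the oximeter limit what an unblinded collector could do, and the calculation agrees that shifts of 1 to 2.5 s do little. It does not answer the main point, because the one safeguard offered does not deliver the blind that is claimed.

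Several stronger readings are tempting and are not supported:

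- *The collector is unblinded.* The documents do not say that the collector sees the valve; they leave it open.
- *The primary result is seriously biased.* An assumed shift of 10 s, one recording interval, would put the type I error at about 15%. Nothing in the documents suggests an average systematic shift of that size.
- *The labels unblind the collector.* They go on the medical record, and no section says that the collector handles it. This is a possible route, not a demonstrated one.
- *The unblinded lead researcher records the data.* The student and the independent researcher may be the same person, and the third description comes in a sentence mainly about custody of the forms. The wording needs reconciling but does not establish this.
- *Complications are open to the same bias.* No section says that the collector, and not the clinicians, identifies them, so the point is not extended to them.

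**Conclusion.** The concern holds as a gap between a stated blind and the means given to achieve it. For Time 1 the blind is not secured. For Time 2 the one-sided closure of the valve can reveal the group as the clock starts. Time 2 also follows ventilation by staff who know the group, which no masking of the collector can remove.

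The size and direction of any bias are unknown. For Time 1 it is probably small: type I error of 5.1% to 7.5%, or power of 88% down to 79%, for assumed average shifts of 1 to 5 s. Those figures rest on 32 analysed per group, the planning SDs, a two-sided normal test and a shift that the documents do not report. That the valve positions differ throughout Time 1 rests on the inference in Step 1.

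The point is worth correcting because the remedy is cheap and because a claim of blinded assessment should be one that the protocol supports.

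**What to change.** 1. State where the collector stands, or what screen is used, so that the valve and any airway-pressure reading are out of view while the oximeter, capnograph and chest remain visible.
2. Take the allocated group off the medical-record label and use the study identification number alone.
3. Name the blinded collector as the person who records Time 1 and Time 2, and reconcile the three descriptions of who completes the form.
4. Where the valve or its closure cannot be hidden, say so in the protocol and report that the affected outcome, notably Time 2, was not assessed blind. The documents do not show whether it can be hidden.

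The cost is a screen or a changed position, reprinted labels and a few sentences of protocol text. Time 2 may have to be reported as unblinded, and the clinical staff remain aware of the group. Nothing in the care of the children changes.

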In patients without comorbidities, candidates for major surgery, the longer apnea before desaturation and the highest PaO₂ values in those who received CPAP during anesthetic induction were significant. The use of CPAP also reduced the time to return to normal baseline saturation after apnea²⁹.

The use of CPAP was also related to higher PaO₂ and lower carbon dioxide blood pressure values (PaCO₂) in obese in anesthetic induction. There were no episodes of hypoxemia in these patients, unlike those who did not use the continuous positive pressure technique³⁰.

The aim of this study is to evaluate the effectiveness of CPAP during anesthetic induction in increasing apnea time until hemoglobin saturation drops to 95% in children undergoing general anesthesia for elective surgery.

Primary hypothesis

- The use of CPAP in preschoolers' pulmonary ventilation during general anesthesia induction for elective surgery delays the occurrence of oxyhemoglobin desaturation during apnea.

Secondary hypotheses

- Oxyhemoglobin saturation values in pulse oximetry in apneic patients in similar periods during anesthetic induction are higher in those using CPAP;
- Time to recovery of normal oxyhemoglobin saturation levels in pulse oximetry after apnea is shorter in patients using CPAP;
- The frequency of complications (laryngospasm, hypoxemia, bradycardia, cardiopulmonary arrest, death) is lower in patients using CPAP.

General objective

To evaluate the effectiveness of CPAP during anesthetic induction in increasing apnea time until hemoglobin saturation drops to 95% in children undergoing general anesthesia for elective surgery.

Specific objectives

In children undergoing general anesthesia for elective surgery who will undergo CPAP or standard circular circuit ventilation during anesthetic induction, compare:

PRIMARY OUTPUT:

The time between onset of apnea and 95% drop in oxyhemoglobin saturation between groups.

Secondary Outcome:

Oxyhemoglobin saturation values on pulse oximetry during anesthetic induction at different times between groups;

Time to recovery of oxyhemoglobin saturation levels in pre-apnea pulse oximetry between groups;

The frequency of complications (laryngospasm, hypoxemia, bradycardia, cardiopulmonary arrest, death) between the groups.

Study Design

This is a randomized, phase III, parallel clinical trial in pediatric patients undergoing elective surgery.

Study site

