The study will be developed in the operating room of the Clinical Hospital of the Federal University of Pernambuco (HC-UFPE).

The HC-UFPE Pediatric Surgery Service performs about 15-20 surgeries per week on an elective basis; The team consists of six surgeons and three resident physicians; and has a room in the operating room in four weekly shifts where it performs procedures on children from birth to 18 years.

Study Period

The study will be conducted from January 2018 to June 2018.

Study Population

Preschool pediatric patients undergoing elective surgery in the operating room of Hospital das Clínicas.

Sample

Sampling

A non-probabilistic convenience sample will be obtained, composed of preschool children who will be submitted to general anesthesia for elective surgery, following the inclusion and exclusion criteria of the study.

Sample size

Sample size calculation was performed using Openepi software, version 3.01 (Dean AG, Sullivan KM, Soc. MM. OpenEpi: Open Source Epidemiologic Statistics for Public Health, Version. www.OpenEpi.com, updated 2013/04/06, accessed 2017/07/11), using difference of means. The first parameter used was the mean time in apnea that patients exposed to the intervention took to achieve a pulse oximetry oxygen saturation of 95% (166 ± 47 seconds) 20. The second parameter was the average time in apnea that patients not exposed to the intervention took to reach a pulse oximetry oxygen saturation of 95% (131 ± 39 seconds) 20. Considering a significance level of 5% and a power of 90%, 64 patients (32 in each group) will be needed. However, with possible losses due to post-randomization exclusion (around 10%), this number will be increased to 72 (36 in each group).

Randomization Procedure

The randomization table will be generated on the computer using the Random Software Allocation program. After randomization, opaque envelopes numbered sequentially from 1 to 72 will then be prepared according to the random number table. The allocation concealment will be respected.

Criteria and procedures for selecting, capturing and following participants

Inclusion criteria

Preschool children;

ASA I or II;

Children undergoing general anesthesia for elective surgery;

Exclusion Criteria

Pre-existing parenchymal lung disease;

Cyanotic or oxyhemoglobin-saturated children less than 95% before anesthetic induction;

Recent history (<4 weeks) or duration of upper respiratory tract infection;

Participant Capture and Follow-Up Procedures

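### Does the two-part stopping point for Time 2 (100% or the child's own pre-apnea SpO2) leave the recovery outcome undefined or biased between arms?

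*Combined protocol and SAP*

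**What the plan says.** In the combined protocol and SAP, under Data collect, Time 2 starts when SpO2 has been recorded at 95% and assisted ventilation begins. The clock then runs "until pulse oximetry reading of the value of 100% or the value obtained immediately before the beginning of apnea". The Secondary Outcome list gives one target only: "Time to recovery of oxyhemoglobin saturation levels in pre-apnea pulse oximetry between groups". The Dependent Variables list gives the same one: "Time to recover oxyhemoglobin saturation levels in pre-apnea pulse oximetry (Time 2". The secondary hypothesis speaks of normal levels. The introduction, describing an adult study, says that CPAP "reduced the time to return to normal baseline saturation after apnea", so the authors treat normal and baseline as the same thing.

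The envelope is opened ahead of entry to theatre (Participant Capture and Follow-Up Procedures), and CPAP Realization states: "In both groups, patients will spontaneously ventilate from the outset with the technique defined at the time of allocation". The pre-apnea reading is therefore taken after randomisation and under the allocated pressure. The only saturation limit at entry excludes "oxyhemoglobin-saturated children less than 95% before anesthetic induction".

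During apnea, SpO2 is "recorded for a maximum time limit of five minutes". No matching limit is given for recovery. Data analysis offers the t-test or Mann-Whitney for two independent samples and has no rule specific to Time 2. A separate secondary outcome is "Oxyhemoglobin saturation values on pulse oximetry during anesthetic induction at different times between groups".

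**The concern.** Two things look wrong. First, the stopping point offers two values joined by a bare or, while the outcome and variable lists offer one. For a child who was at 98% before apnea, the clock might stop at 98% or at 100%.

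Second, the child's own value is measured after allocation. The plan's rationale is that CPAP improves gas exchange, so a higher pre-apnea SpO2 in the CPAP arm is plausible. Recovery always starts from 95%, so a higher target means a longer climb. The CPAP arm could then show a longer Time 2 with no difference in recovery speed, and a true benefit would be understated.

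There is also no stated end of observation for a child who does not regain the target. At stake is the between-group comparison of one secondary outcome.

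**Working it through.** **The plan's own figure.** The documents give no figure for Time 2. The only sample-size calculation is for the primary outcome, and it reproduces. With means 166 and 131 s, SDs 47 and 39 s, two-sided 5% and 90% power (Sample size): (47² + 39²) × (1.960 + 1.282)² / 35² = 31.99, so 32 per group. Then 32 / 0.9 = 35.6, so 36 per group and 72 in total. Nothing in the Time 2 definition enters it.

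**Which value ends the clock.** Let b be the child's pre-apnea SpO2, with b at most 100.

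| Reading of the stopping point | Target | Agrees with Secondary Outcome and Dependent Variables? |
|---|---|---|
| 100%, or the child's own value if lower | b | Yes |
| Whichever is reached first | min(100, b) = b | Yes |
| 100% for every child | 100 | No |

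The first two readings give the same number. The third contradicts two other sections and leaves the second half of the phrase with no purpose. It would change the climb from 3 to 5 points for b = 98, from 4 to 5 for b = 99, and not at all for b = 100.

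**How far the target could differ by arm.** The documents give no pre-apnea SpO2, so everything here is assumption. Let a share p of an arm be at 100% and the rest at 99%. The mean climb from 95% is 5p + 4(1 − p) = 4 + p points. With a constant rate of rise and no delay, the ratio of mean times equals the ratio of climbs:

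- each 10-percentage-point difference in p: 4.1/4.0 = 1.025 to 5.0/4.9 = 1.020;
- 90% against 70% at 100%: 4.9/4.7 = 1.043;
- all at 100% against all at 99%: 5/4 = 1.25;
- equal distributions: 1.00.

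If the rest are at 98%, the mean climb is 3 + 2p. Then 90% against 70% gives 4.8/4.4 = 1.09, and 90% against 50% gives 4.8/4.0 = 1.20.

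**With a delay before SpO2 rises.** Any delay common to both arms shrinks these ratios. Assume 10 s, then 0.5 points per second. With the rest at 99%, mean time is 10 + (4 + p)/0.5 = 18 + 2p s:

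- each 10-percentage-point difference in p: 0.2 s (ratio 1.010 to 1.011);
- 90% against 70%: 19.8 against 19.4 s, a difference of 0.4 s;
- all at 100% against all at 99%: 20 against 18 s, a difference of 2 s (ratio 1.11).

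With the rest at 98%, mean time is 10 + (3 + 2p)/0.5 = 16 + 4p s, and 90% against 70% gives 19.6 against 18.8 s, a difference of 0.8 s. The differences in seconds scale inversely with the assumed rate: at half the rate they double. The no-delay ratios are the ceiling for each scenario at any rate.

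**The case for a change.** The strongest case for acting is that the fault is real on the text and cheap to cure. No selection rule is written, and reading the phrase as whichever comes first does not remove the dependence on arm, because it leads back to the post-allocation value. During recovery the Open System valve is closed to the same 10 cmH2O as in the CPAP group, so the true contrast may be small and a modest artefact could count for more. The data collector is in the room when that happens and may infer the group just as the stopping rule is applied. One SpO2 value common to all children, with censoring and a log-rank test, would settle all of this.

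Some of this stands. The target is a post-randomisation value, and a difference between arms cannot be ruled out. But return to the child's own level is the outcome the plan names, and for that quantity a longer climb from a higher baseline is part of what is measured. A common threshold answers a different question, and statisticians could reasonably prefer either.

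The collector's discretion is small once the phrase is read in line with the outcome list, because the endpoint is a number on a monitor.

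The missing end of observation is a gap, but no section suggests that these ASA I or II children, without parenchymal lung disease or recent respiratory infection, would fail to recover under assisted ventilation from 95%. If one did, the analyst could report the case and rank it last in the Mann-Whitney test the plan already allows.

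A child still above 95% at five minutes has no defined Time 2 start, and a common threshold would not mend that. On the planning figures it is rare: 300 s lies (300 − 166)/47 = 2.85 SDs above the intervention mean and (300 − 131)/39 = 4.33 above the control mean. If times are normal, that is about 0.2% of the intervention arm, or 0.08 of 36 children.

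**Conclusion.** No change to the plan is needed. The bare or is loose drafting, and two other sections resolve it: Time 2 is the return to the child's own pre-apnea value, which is 100% for a child who was at 100%. A clarifying clause would be tidy, but its absence does not make the result unsound. This concerns only when timing stops and has no bearing on ventilation.

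The possible imbalance in targets is undemonstrated. It is zero if all children read 100% before apnea, which induction at 60.5% oxygen makes plausible for many. Under the assumed delay and rate it is 0.2 s per 10-percentage-point arm difference in the share at 100%, and 2 s at the extreme, if no child is below 99%. It would be larger with lower pre-apnea values or slower recovery. If CPAP raises pre-apnea SpO2, as the plan's rationale suggests, the effect is conservative and cannot manufacture a benefit. If the Open System arm had the higher values, it would run the other way.

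A reader will be able to judge this, because the pre-apnea value has to be recorded to time Time 2, and saturation during induction is already compared between groups. Tabulating the pre-apnea value by arm is ordinary reporting. Replacing the stated outcome with a common threshold and a log-rank test would change the estimand for no clear gain.

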Upon completion of the entry of all forms in the database, the final revision will be performed and the missing data will be completed by the above mentioned processes. The definitive database thus created will then be used for statistical analysis in the STATA program, being also submitted to tests of consistency and cleaning of the information, generating backups.

Data analysis

Data analysis will be performed by the researcher and the responsible statistician (supervised by her advisor), using the STATA program.

Descriptive statistical analysis will be performed through measures of central tendency and dispersion for quantitative variables and frequency distribution for qualitative variables. For comparison of paired samples, a non-parametric method, Wilcoxon's t-test will be used.

Student's t-test will be used for two independent samples, previously considering the Kolmogorov-Smirnov normality test for each sample, and for non-normality, the nonparametric Mann-Whitney U test will be used. Quantitative variables according to the time of their performance will be used analysis of variance for repeated units (ANOVA), if they present a normal distribution, or Wilcoxon if normality is not present. For categorical variables, Fisher's exact test or Chi-square will be used when necessary.

Relative Risk and its 95% confidence interval, in addition to the Number Needed to Treat and Benefit (NNT) or the Number Needed to Treat or Harm (NNH) where relevant, will also be calculated.

Ethical aspects

The research will respect human rights and the principles of bioethics (Autonomy, Non-Maleficence, Charity, Justice and Equity). Confidentiality and confidentiality in the collection and archiving of collected data will be respected.

The terms of National Council of Health Resolution No. 466 of December 12, 2012 for human research will be followed as well as the Declaration of Helsinki. In addition, the project will be submitted to the Research Ethics Committee of the proposing institution, the data will only be collected after such submission and approval of the committee, and the children of the study will only be included after the parents or guardians have signed the free and informed consent form. Clarified (IC, Appendix 2).

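### SpO2 over time is a between-group secondary outcome, but its non-normal fallback is a test the plan uses for paired samples, and no rule covers children who have already reached 95%

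*Combined protocol and SAP*

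**What the plan says.** Under Secondary Outcome the protocol lists "Oxyhemoglobin saturation values on pulse oximetry during anesthetic induction at different times between groups". The matching secondary hypothesis is "Oxyhemoglobin saturation values in pulse oximetry in apneic patients in similar periods during anesthetic induction are higher in those using CPAP". The design is parallel-group, so this is a contrast between independent arms.

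Under CPAP Realization, readings are taken every 10 seconds after apnea begins, and "the oxyhemoglobin saturation through the pulse oximeter will be recorded for a maximum time limit of five minutes". Data collect says when the apneic phase ends: "The measurement will take place until the pulse oximetry is recorded at 95%. Assisted ventilation will then be instituted". A second timer then starts: "At this time, there will be a new timing of the time until pulse oximetry reading of the value of 100" per cent or the pre-apnea value.

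Data analysis assigns methods by type of variable and does not list outcomes. It introduces Wilcoxon with the words "For comparison of paired samples, a non-parametric method". For two independent samples it gives Student's t-test or, if not normal, Mann-Whitney U. For quantitative variables over time it gives "analysis of variance for repeated units (ANOVA), if they present a normal distribution, or Wilcoxon if normality is not present". This last sentence does not name SpO2, but SpO2 is the only listed outcome measured at different times.

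The only text on missing data, under Data Processing, is about going back to archived forms to correct or complete entries. It is not an analysis rule.

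**The concern.** There are two gaps.

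- **The test.** If Wilcoxon has the meaning the section gave it a few lines earlier, the fallback compares readings within a child. It cannot compare CPAP with open system, which is what the secondary hypothesis needs. The fallback may well be used, because SpO2 cannot exceed 100% and the apneic phase ends at 95%.
- **The children who have left apnea.** Once a child reaches 95%, there is no apneic SpO2 at later times. The plan does not say whether such a child is dropped, held at 95%, or represented by readings taken under assisted ventilation. If children are dropped, each later comparison is restricted to those with a long time to 95%. That is selection on the primary outcome, and if CPAP works it removes more children from the open arm.

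With both points open, the test, the time points and the children compared could all be settled after the data are seen.

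**Working it through.** **Inputs (Sample size section).** Time to 95%: intervention 166 ± 47 s, described as "the mean time in apnea that patients exposed to the intervention took to achieve a pulse oximetry oxygen saturation of 95" per cent; control 131 ± 39 s. Significance level 5%, power 90%, 32 per arm, raised to 36.

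**The plan's own figure.** n per arm = (47² + 39²)(1.960 + 1.282)² / 35² = 3730 × 10.51 / 1225 = 31.99, so 32 per arm and 64 in total. Dividing by 0.9 for losses gives 32 / 0.9 = 35.6, so 36 per arm and 72 in total. The stated size reproduces as a two-sided calculation, and nothing below changes it.

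**Children who have reached 95% by time t.** Taking times as normal, the share is Φ((t − mean)/SD).

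| t | Open: z, share | CPAP: z, share | Still apneic of 32, open vs CPAP |
|---|---|---|---|
| 60 s | −1.82, 3.4% | −2.26, 1.2% | 30.9 vs 31.6 |
| 120 s | −0.28, 38.9% | −0.98, 16.4% | 19.6 vs 26.8 |
| 150 s | 0.49, 68.7% | −0.34, 36.7% | 10.0 vs 20.3 |

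With lognormal times of the same means and SDs, the shares are 44% vs 15% at 120 s and 73% vs 41% at 150 s.

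**What the selection does to the planned contrast.** Among children still apneic at t, the mean time to 95% is m + s·φ(a)/(1 − Φ(a)), with a = (t − m)/s.

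| t | Open | CPAP | Gap | Gap, lognormal |
|---|---|---|---|---|
| All children | 131 s | 166 s | 35 s | 35 s |
| 60 s | 134.1 s | 167.5 s | 33.4 s | 34.6 s |
| 120 s | 155.5 s | 179.9 s | 24.4 s | 20.1 s |
| 150 s | 175.1 s | 193.9 s | 18.8 s | 13.8 s |

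This needs no SpO2 curve. It shows that the children left at 120 s and 150 s are more alike across arms than the randomized groups, while at 60 s they are nearly the randomized groups.

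**Translation to SpO2 (illustration only).** This needs a desaturation curve, which the documents do not give. Assume SpO2 = 100 − 5(t/T)^k, with T the time to 95%, k from 1 to 4 and normal times. The 120 s difference is then 0.48 to 0.77 points among still-apneic children, against 0.64 to 1.27 points if those who have reached 95% are held at 95. The direction is stable over these curves; the size is not.

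**The case against.** **Wilcoxon may mean rank-sum.** That test is equivalent to Mann-Whitney. The plan also assigns Mann-Whitney generically to two independent samples, and SpO2 at one time in two arms is such a case. A reader might infer that the trial has no valid non-normal test for this outcome. The documents do not support that: it is true only if Wilcoxon is read as paired. What stands is that the section uses the two names for different designs and gives the over-time variables the paired one.

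**Post-ventilation readings are probably already out.** The hypothesis is limited to apneic patients, and recovery has its own timer. A reader might infer that the plan mixes rescued and apneic readings; it does not say so. What stands is that the analysis section does not state the exclusion, and that exclusion alone leaves the selection at later times.

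**Loss of power.** It is tempting to conclude that a real benefit would most likely be missed at late times if only still-apneic children are compared. The documents do not support a figure for this:

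- Any such figure needs assumed curves and reading noise. In one illustration (k = 1, 120 s), adding noise with an SD of 1 point lowers power from about 58% to 23% among still-apneic children, and from about 85% to 66% with rescued children ranked lowest.
- Still-apneic and lowest-rank analyses answer different questions. At 150 s, a comparison of reached-95%-or-not, with no SpO2 values, already has about 76% power on the planning figures. Most of the lowest-rank method's strength there therefore re-tests the primary outcome.

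**Conclusion.** The concern holds as two gaps in the specification of one secondary outcome. Read as the section itself uses the name, the non-normal fallback cannot compare the arms; if rank-sum was meant, the text needs to say so. The absence of a rule after 95% also matters. On the planning figures, 39% vs 16% of children have left apnea by 120 s and 69% vs 37% by 150 s, so a still-apneic comparison at those times is selected on the primary outcome.

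The percentages and gaps rest on the Sample size figures and on normal times to 95%; lognormal times give the same picture. The effect on SpO2 differences and on power cannot be fixed from the documents. Nor should the small loss of children at 60 s be read as proof that SpO2 comparisons there are sensitive, since that too depends on the curve.

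The primary outcome and N=72 are unaffected. Severity is minor to moderate.

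**What to change.** In Data analysis, replace Wilcoxon for SpO2 over time with the following, settled before the data are seen:

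1. Mann-Whitney U between CPAP and open system at a small set of apnea times fixed in advance.
2. A multiplicity method across those times, or a statement that the results are descriptive.
3. A statement that readings after assisted ventilation starts are excluded.
4. Children who have already reached 95% are given the lowest rank (tied) and are not dropped.
5. A label for times from about 120 s onward: a composite of SpO2 and having reached 95%, which largely repeats the primary outcome. Interpretation of SpO2 itself should rest on early times, when nearly all children are still apneic.

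The cost is wording only, because the 10-second readings are already scheduled and no procedure changes. There are two downsides. The late comparisons add little beyond the primary outcome. The early ones may show only small differences if saturation stays flat before it falls: under the assumed curves tried (normal times, k up to 8 or a linear fall over the last 30 s), the 60 s difference with rescued children held at 95 was 0.19 to 0.52 points.
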